Diagnostic Accuracy of Using
Colonoscope with Near Focus
Capability in Detecting Residual
Colorectal Neoplastic Tissue
After EMR: A Prospective Study

NCT# 02668198

December 3, 2015

IRB Minimal Risk Protocol Template

General Study Information

Principal Investigator: [name] MPH

Study Title: Diagnostic accuracy of using colonoscope with near focus capability in detecting residual colorectal neoplastic tissue after EMR: a prospective study

Protocol version number and date:

Purpose

Hypothesis:

Using standard white light with and without near focus does not provide better sensitivity and negative predictive value compare to narrow band imaging with and without near focus when assessing previous endoscopic mucosal resection (EMR) site for residual neoplasia

Aims, purpose, or objectives:

- Compare the accuracy of using different endoscopic imaging technique (white light, white light with near focus, narrow band imaging (NBI), NBI with near focus) for detection of residual neoplastic tissue at site of prior EMR

Background (*Include relevant experience, gaps in current knowledge, preliminary data, etc.*):

Residual neoplasia after EMR is a common. Optimal surveillance protocols are not clearly defined. There is a need for better imaging modalities to evaluate for residual disease. Suspected residual tissue can be confirmed with repeat colonoscopy or can be empirically treated. However, this can lead to either frequent colonoscopy or overtreatment. This presents more cost and financial burden to the patient. With the introduction of newer colonoscopes that have near focus/zoom capability, it is important to assess whether the near focus technology offers better accuracy for detection of residual neoplastic tissue. With better accuracy to confidently rule out residual neoplasia using newer imaging modality, additional treatment or biopsy at the previous EMR may be avoided. Furthermore, the interval for surveillance colonoscopy can be lengthened.

Subject Information – charts, records, images, or specimens are considered ‘subjects’

Target accrual is the proposed number of subjects to be included in your study at your site. “Subjects” may include Mayo Clinic charts, records, or specimens, and/or charts, records, or specimens received at Mayo Clinic from external sources for collaborating analysis by the investigator under this IRB application:

Target accrual: 200 Patients

Subject population:

Patients who need to undergo follow-up colonoscopy 6 months after initial EMR procedure will be enrolled at one tertiary-care referral institution

Inclusion Criteria: Post-EMR follow up at 6-12 months

Exclusion Criteria:

- Non-corrected coagulopathy
- Pregnancy
- Breast feeding

Yes No Will a Certificate of Confidentiality (COC) be obtained from NIH? If yes,

Who is obtaining the COC: Mayo Clinic investigator, study sponsor, other:

Explain why a COC is needed:

Study Design

Methods: Describe, in detail, the research activities that will be conducted under this protocol:

Methods

This is a prospective, comparison trial. Patients who need to undergo follow-up colonoscopy 6 months after initial EMR procedure will be enrolled at one tertiary-care referral institution. Colonoscopies will be performed by four different endoscopists. All procedures will be performed by using a high-definition colonoscope (Olympus CFH190) with the near focus mode capability. For the 190 systems, the polyp was examined in standard focus and near focus modes, which provided in-focus images up to 2 mm from the optical lens, thus allowing true optical, in-focus zoom.

One type of colonoscope will be used for each patient. No additional endoscope will be utilized for the study. All patients will undergo general anesthesia for the procedure, and this is the standard of care for all patients undergoing EMR. Little additional time (less than 5 minutes) will be needed for the endoscopist to examine the area using the different endoscopic imaging methods and take biopsies if needed.

Prior to study start, all EMR endoscopists will review a test set of images (10) including those with and without residual neoplasia. They will then be tested on an independent set of 10 images. A score of 90% or higher is required prior to starting participation in the study.

Different endoscopic imaging methods will be utilized to identify and evaluate the previous EMR resection site. The scar site will be examined for the presence or absence of residual neoplasia. The prior EMR site will be evaluated using 1) high definition white light, 2) white light with near focus, 3) NBI, and 4) NBI with near focus in real time. Endoscopic images are taken using each of the endoscopic imaging methods. A total of at least four photographs will be taken for each subject to be reviewed offline blinded to histopathology. While using imaging techniques to examine the previous EMR site, the endoscopist will also be required to take a questionnaire during the procedure.

One, does the endoscopist have suspicion of residual tumor at the site (yes/no).

Two, does the endoscopist have high or low confidence of his/her assessment.

[name] and other research assistants of [name] will be administering and recording the questionnaire during clinical procedure at Mayo Florida.

Research coordinators and assistants of [name] [name] will be administering and recording the questionnaire during clinical procedure at Mayo Rochester.

Research coordinators and assistants of [name] will be administering and recording the questionnaire during clinical procedure at Mayo Arizona.

After careful inspection of the previous EMR site, at least four biopsies will be taken at the site to assess for any evidence of residual neoplasia. All resected specimens will undergo standard histopathology assessment by one pathologist who is blinded to the prior endoscopic imaging information.

The following information are collected prospectively from study participants

- Patient demographics
- Date of original procedure EMR
- Piecemeal/En Bloc procedure/Paris and Kudo classification of EMR scar
- Location of the previous EMR
- Size of the lesion
- Follow up date
- Follow up location
- White light (Positive or negative)
- White light near focus (Positive or negative)
- NBI diagnosis (Positive or negative)
- NBI with near focus (Positive or negative)
- Suspicion (high or low for each imaging technique)
- Prior clip placed and number of clip placed
- Histopathology diagnosis (positive or negative)

Other than the original endoscopist who performs the original surveillance colonoscopy, other gastroenterologists will evaluate the photographs that were taken using different endoscopic imaging techniques and assess for evidence of residual neoplasia. Same questionnaire will also be utilized. The gastroenterologists are blinded to the histopathologic diagnosis.

Resources: *Describe the available resources to conduct the research (personnel, time, facilities, mentor commitment, etc.):*

Setting

Tertiary-care referral hospitals (MCF, MCA, and MCR)

Check all that apply. If none apply, leave blank:

This is a multisite study involving Mayo Clinic and non-Mayo Clinic sites.
When checked, describe the research procedures/activities being conducted **only** at Mayo Clinic:

Mayo Clinic staff will be engaged in research activity at a non-Mayo Clinic site. *When checked, provide the location and a detailed description of the Mayo Clinic research staff involvement.*

This study is to establish and/or maintain an ongoing database or registry for research purposes only.

The research involves contact or interaction with subjects, for example, surveys, questionnaires, observation, blood draw.

The study involves photographing, audiotaping or videotaping subjects (and guests).

Blood Collection

If this study involves prospective blood collection by finger, heel, ear stick or venipuncture, complete the following:

From healthy, non pregnant, adult subjects who weigh at least 110 pounds. For a minimal risk application, the amount of blood drawn from these subjects may not exceed 550ml in an 8 week period and collection may not occur more frequently than 2 times per week.

Volume per blood draw: _____ ml

Frequency of blood draw (e.g. single draw, time(s) per week, per year, etc.) _____

From other adults and children considering age, weight, and health of subject. For a minimal risk application, the amount of blood drawn from these subjects may not exceed the lesser of 50 ml or 3 ml per kg in an 8 week period, and collection may not occur more frequently than 2 times per week.

Volume per blood draw: _____ ml

Frequency of blood draw (e.g. single draw, time(s) per week, per year, etc.) _____

Review of Chart, Images, Specimens

Provide the date range for collection of data and/or specimens that will be included in your research dataset.

Example: 01/01/2000 to 12/31/2013 or all records through mm/dd/yyyy.

For a retrospective chart review, enter the date range:

Check all that apply:

- This study involves only data and/or specimens that exist at the time this application is submitted to the IRB (IRB submission date). No data or specimens will be collected beyond this date.
- This study involves only data and/or specimens that will be collected after submission to the IRB.
- The study involves data and/or specimens that exist at the time of submission to the IRB **and** data and/or specimens that will be collected after submission to the IRB, for example a study that includes collection of existing data and prospective collection of specimens.
- Data and/or specimens used in this study are collected under another IRB protocol. *When checked, provide the IRB number(s) from which the research material will be obtained. When appropriate, check the box below to attest that subjects have provided consent for future use of their data and/or specimens, as described in this protocol.*

IRB Number/s - Data Only: _____

IRB Number/s - Specimens Only: _____

IRB Number/s - Data and Specimens: _____

Note: When subjects provided consent for use of their data and/or specimens, as described in this protocol.

- Other data sources will be utilized in this study, e.g. receiving data/specimens from an external party. When checked, provide all data sources:

Data Confidentiality, HIPAA Subject Identifiers

Review the list of subject identifiers below and, if applicable, check the box next to each subject identifier being recorded at the time you are collecting/abstracting data/specimens for use in this study.

Subject Identifiers: Individually identifiable information, including demographic data, that identifies the individual or for which there is reasonable basis to believe it can be used to identify the individual. NOTE: Identifiers apply to subjects enrolled in your study and to the subject's relatives, household members, employers, etc.

Internal refers to subject identifiers that will be included in the dataset maintained by the study team.

External refers to subject identifiers that will be shared with persons outside of the immediate study team, for example, sent to an external collaborator or shared with a national registry.

SUBJECT IDENTIFIERS Check all that apply	INTERNAL IDENTIFIER	EXTERNAL IDENTIFIER
Name	x	
Social Security number		
Medical record/patient registration number, lab accession, specimen or radiologic image number	x	
Study number, subject ID, or any other unique identifying number, characteristic or code that can be used to link the identity of the subject to the data	x	
Dates: All elements of dates [month, day, and year] directly related to an individual. Their birth date, date of death, date of diagnosis, etc. Note: Recording a year only is not a unique identifier.	x	
Medical device identifiers and serial numbers		
Biometric identifiers, including finger and voice prints, full face photographic images and any comparable images		
Web Universal Resource Locators (URLs), Internet Protocol (IP) address numbers, email address		
Street address, city, county, precinct, zip code, and their equivalent geocodes		
Phone or fax numbers		
Account, member, certificate or professional license numbers, health beneficiary numbers		
Vehicle identifiers and serial numbers, including license plate numbers		
If None of the above identifiers will be recorded or maintained in the dataset and/or sent outside of the study team, please check "None".	 None	 None

Statistical Information

Note: Power analyses and study endpoints are not needed for a pilot or feasibility studies.

No statistical information. *If checked, please explain:*

Statistical Considerations

Power Statement:

Sample size is estimated based on the degree of precision. We estimate that 20% of cases will have residual neoplasia. Thus, sensitivity will be the key limiting variable. In order to achieve confidence intervals < 5%, assuming 90% sensitivity, 150 cases are needed. To account for possible drop out, lower quality images, or inability to get 4 high quality images in all cases, we will enroll 200 patients.

Data Analysis Plan:

Endpoints

Primary:

Sensitivity, specificity, accuracy for white light, white light with near focus, NBI, and NBI with near focus against histopathology as the standard reference.

Secondary:

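### Does the conditional biopsy wording in Methods leave image-negative scars without a reference standard?

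*Combined protocol and SAP*

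**What the plan says.** The Combined protocol and SAP mentions biopsy at the follow-up examination twice under Study Design, Methods.

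- The paragraph on the colonoscope, anaesthesia and procedure time puts the added time at under 5 minutes and says the endoscopist will use it to "examine the area using the different endoscopic imaging methods and take biopsies if needed".
- The later account of the examination, after the four imaging modes and the questionnaire, says that following inspection "at least four biopsies will be taken at the site to assess for any evidence of residual neoplasia". It continues: "All resected specimens will undergo standard histopathology assessment by one pathologist who is blinded to the prior endoscopic imaging information".

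Three other places bear on the point. The list of prospectively collected items gives the histopathology result two values, positive and negative. The primary endpoints are sensitivity, specificity and accuracy of each imaging mode "against histopathology as the standard reference". The Power Statement raises 150 cases to 200 "To account for possible drop out, lower quality images, or inability to get 4 high quality images in all cases". The available text breaks off at the secondary endpoints.

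**The concern.** Read on its own, the first sentence makes biopsy conditional, and the natural guess is that need would be judged from the image. The second sentence has no condition. The document defines neither what need means nor which sentence prevails, and it names no code for a scar without histology.

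The reference standard is what is at stake. If scars negative on imaging were biopsied less often, missed residual neoplasia would drop out of the sensitivity denominator and true negatives would drop out of specificity. The Hypothesis names sensitivity and negative predictive value (NPV), and the Background hopes that "additional treatment or biopsy at the previous EMR may be avoided". That use needs histology from image-negative scars. Several endoscopists take part and questionnaires are recorded at three Mayo sites, so different readings of one phrase are conceivable.

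**Working it through.** **1. The passages side by side.** The time sentence describes burden. It gives no number of biopsies and no trigger, and does not link biopsy to a positive image. The procedural sentence gives a minimum number, a location, a point in the sequence (after inspection) and a purpose (looking for any residual neoplasia). Blinding the pathologist to imaging, a histology result listed among the items collected from participants, and histopathology as reference for all primary endpoints all presuppose histology at every site. The sample-size allowance covers drop-out and image quality, with nothing for unbiopsied scars. Each of these fits the procedural sentence.

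**2. What a departure would do.**

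Inputs from the Power Statement: 150 cases, prevalence 20%, sensitivity 90%. Assumed, because the available text gives no figure: specificity (90%, with 80% as a variant) and the share f of image-negative scars biopsied. The 150 serves only as a scale, giving 150 × 0.20 = 30 diseased and 120 disease-free sites. How the plan arrives at 150 is a separate question that this point does not depend on.

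*One imaging result decides biopsy; unverified scars excluded.* TP = 30 × 0.90 = 27; FN = 3f; FP = 120 × (1 − Sp); TN = 120 × Sp × f.

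| f | Sp assumed | Sensitivity | Specificity | Accuracy | NPV |
|---|---|---|---|---|---|
| 1 (every site biopsied) | 90% | 27/30 = 90.0% | 108/120 = 90.0% | 135/150 = 90.0% | 108/111 = 97.3% |
| 0.5 | 90% | 27/28.5 = 94.7% | 54/66 = 81.8% | 81/94.5 = 85.7% | 54/55.5 = 97.3% |
| 0.5 | 80% | 27/28.5 = 94.7% | 48/72 = 66.7% | 75/100.5 = 74.6% | 48/49.5 = 97.0% |

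The first row is the plan as its procedural step reads: no bias. With specificity 80% and every site biopsied, accuracy would be (27 + 96)/150 = 82.0% and NPV 96/99 = 97.0%, so NPV is unchanged in both variants.

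*Four modes; biopsy if any is positive.* Let d0 and h0 be the probabilities that all four modes are negative in a diseased and in a disease-free scar, and v the share of all-negative scars biopsied. With unverified scars excluded:

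- apparent sensitivity = Se / [1 − d0(1 − v)]
- apparent specificity = 1 − (1 − Sp) / [1 − h0(1 − v)]

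Assume Se = Sp = 0.90 for all four modes and an equicorrelated latent-normal model with correlation 0, 0.5, 0.8 or 0.9. Then d0 = 0.0001, 0.0091, 0.0328, 0.0494 and h0 = 0.656, 0.741, 0.807, 0.837. At v = 0.5:

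- sensitivity 90.0, 90.4, 91.5, 92.3%
- specificity 85.1, 84.1, 83.2, 82.8%

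For example, at correlation 0.8, sensitivity = 0.90/(1 − 0.0328 × 0.5) = 0.915. At v = 1 both formulas return the true values.

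The sensitivity denominator is the same for every mode, so ratios between modes are preserved: true sensitivities of 80% and 90% have ratio 0.889 before and after.

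**3. Scale against sampling error.** With 30 diseased sites the 95% half-width for 90% sensitivity is 1.96 × √(0.9 × 0.1/30) = 10.7 points. The sensitivity shifts at v = 0.5 are 0 to 2.3 points.

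**The case for a change.** The strongest case for acting is that the contradiction is literal, it touches the reference standard, and histology not taken cannot be recovered later. In the extreme, where no all-negative scar is biopsied and unverified scars are excluded, the four-mode model gives specificity of 70.9% at correlation 0 and 38.7% at correlation 0.9, against a true 90%. With only two values listed for histology, an unbiopsied scar might also be entered as negative. The remedy would cost one sentence and one code.

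The wording mismatch stands, and so does the direction of the bias should biopsy become conditional on imaging. The rest carries less weight. The extreme figures need v = 0, the opposite of the procedural step, together with an assumed specificity, an assumed correlation and a biopsy rule that no section states. A two-value label describes the expected results; it is not a rule for missing histology. An analyst with no histology for a site would treat the reference as missing and report how many such sites there were. Because the available text stops at the secondary endpoints, silence on missing histology cannot be held against the plan. A verification-bias correction would have nothing to correct if the procedural step is followed.

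**Conclusion.** The concern does not call for a change. The two sentences differ, but only one describes the procedure: it takes at least four biopsies at the site without condition, and the blinded histology, data list and primary endpoints all rely on it. Under that step every site is verified and the bias is zero. The conditional phrase is a clerical looseness in an estimate of procedure time. The two sentences can be reconciled whenever the text is next edited, with no effect on conduct or analysis.

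The conclusion assumes that endoscopists follow the procedural step. If some did not, absolute sensitivity could be overstated and, with unverified scars excluded, specificity understated; under an any-positive rule, sensitivity ratios between modes would hold. The documents do not allow the size of such a departure to be estimated. Handling an occasional site without histology is a detail that analysts would fill sensibly.

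### The 150 cases cannot give a sensitivity interval within 5%: at 20% prevalence only about 30 are histology-positive, so the 95% half-width is about 10.7 points

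*Combined protocol and SAP*

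**What the plan says.** The sample size is justified in one short paragraph, the Power Statement under Statistical Considerations. It rests on interval width, not on the power of a test: "Sample size is estimated based on the degree of precision". The next step is a prevalence and its consequence: "We estimate that 20% of cases will have residual neoplasia. Thus, sensitivity will be the key limiting variable". The size follows directly: "In order to achieve confidence intervals < 5%, assuming 90% sensitivity, 150 cases are needed". An allowance for losses is then added: "To account for possible drop out, lower quality images, or inability to get 4 high quality images in all cases, we will enroll 200 patients".

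The accrual figure under Subject Information agrees and is counted in patients: "Target accrual: 200 Patients". Eligibility is not enriched for recurrence: "Inclusion Criteria: Post-EMR follow up at 6-12 months". Sensitivity, with specificity and accuracy, is a primary endpoint for each of the four imaging modes, with histopathology as reference.

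The plan does not state the confidence level, the interval method, or whether the 5% is a half-width or a full width.

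**The concern.** Sensitivity has only the histology-positive scars in its denominator. That is why a low prevalence makes it the limiting quantity, as the plan itself says. Yet the number in the following sentence matches a calculation in which every one of the 150 cases is positive. The premise and the result therefore contradict each other within three sentences.

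Nothing else in the document justifies the size of the study. The Hypothesis turns on sensitivity and negative predictive value, and the Background hopes that better imaging could spare patients biopsy or further treatment and lengthen surveillance intervals. Anyone who approved the study on the stated precision was told that sensitivity would be estimated about twice as precisely as the design allows. An observed 90% would be compatible with a true value near 74%, at which about one residual neoplasia in four would be missed.

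**Working it through.** **Inputs from the Power Statement:** sensitivity p = 0.90; prevalence 0.20; 150 evaluable cases; 200 enrolled, which implies a 25% loss because 150/(1 − 0.25) = 200.

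**Assumptions, because the plan is silent:** two-sided 95% confidence (z = 1.96), and 5% read as a half-width, which is the reading more favourable to the plan.

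**Step 1. Reproduce the plan's figure.** The Wald half-width is z × √(p(1 − p)/n). With n = 150 as the denominator:

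1.96 × √(0.09/150) = 4.80 points.

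This is below 5, so it is probably where 150 comes from. That is an inference, since the plan shows no formula. It is not an exact reproduction either: the smallest n with a half-width below 5 points is 139 (Wald), 141 (Wilson) or 158 (Clopper-Pearson or continuity-corrected Wald). All of these count positive scars, not patients.

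**Step 2. Apply the 20%.**

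| Evaluable patients | Expected positives | Wald half-width | Wilson 95% interval | Clopper-Pearson 95% interval |
|---|---|---|---|---|
| 150 | 150 × 0.20 = 30 | 1.96 × √(0.09/30) = 10.74 points | 27/30: 74.4% to 96.5% | 73.5% to 97.9% |
| 200 | 200 × 0.20 = 40 | 1.96 × √(0.09/40) = 9.30 points | 36/40: 76.9% to 96.0% | 76.3% to 97.2% |

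Against a target of 5 points, the ratio is 10.74/5 = 2.15 with 150 evaluable and 9.30/5 = 1.86 with 200.

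**Step 3. What the target would need.**

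- Positives: 0.09 × (1.96/0.05)² = 138.3, so 139.
- Evaluable patients: 139/0.20 = 695. With the implied 25% loss: 695/0.75 = 927 enrolled.
- If 5% is the full width: 0.09 × (1.96/0.025)² = 553.2, so 554 positives and 554/0.20 = 2,770 evaluable patients.
- Prevalence at which the planned numbers would suffice: 138.3/150 = 92%, or 138.3/200 = 69%.

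**Step 4. Vary the unstated confidence level (Wald half-width in points).**

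| Confidence | 30 positives | 40 positives |
|---|---|---|
| 80% | 7.02 | 6.08 |
| 90% (also one-sided 95%) | 9.01 | 7.80 |
| 95% | 10.74 | 9.30 |
| 99% | 14.11 | 12.22 |

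No entry is below 5.

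**Step 5. The other primary endpoints.** The plan assumes no value for specificity or accuracy. If each were 90% (an assumption), 150 × 0.80 = 120 negatives would give 1.96 × √(0.09/120) = 5.37 points for specificity. Overall accuracy uses all 150 cases and would have the 4.80 points of Step 1.

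**The case against.** The best defence is that the 150 cases are 150 residual neoplasias. The arithmetic would then work, but 150/0.20 = 750 evaluable patients would be needed, and the plan goes straight from 150 to 200 patients to cover losses. The word for cases also plainly means all examined cases in the prevalence sentence.

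Other readings fail too:

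- The offline reading of photographs by other gastroenterologists adds readings of the same scars, not independent positive scars.
- Several scars per patient are not described.
- Taking 5% as one standard error fails with 30 positives (√(0.09/30) = 5.5 points). It passes only if all 200 are evaluable (√(0.09/40) = 4.7 points), and the text speaks of confidence intervals.
- The template exempts pilot studies from a power analysis, but this study does not call itself a pilot.

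Some objections do stand, and they limit what may be claimed:

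- The 95% level is an assumption.
- The shortfall is a little over twofold with 150 evaluable and a little under twofold with 200.
- The wish to rule out residual disease is Background motivation; the listed aim is to compare the accuracy of the four techniques.
- Ruling out also depends on negative predictive value. At 20% prevalence, a sensitivity of 74.4% and an assumed specificity of 80% to 95%, it is 0.64/(0.64 + 0.0512) = 92.6% to 0.76/(0.76 + 0.0512) = 93.7%. So the arithmetic does not show that the study is useless for that purpose, only that sensitivity is estimated far less precisely than stated.

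The study is minimal risk and the correction is one paragraph, which might argue for a milder grading. Against that, the error lies in the only sample-size justification and contradicts that paragraph's own inputs.

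**Conclusion.** The concern holds, and the statement must be corrected. On the plan's own prevalence and sensitivity, the half-width is about 10.7 points with 150 evaluable patients and about 9.3 with 200, roughly twice the stated 5. The two-sided 95% level and the half-width reading are assumptions, but the conclusion does not depend on them: it survives every confidence level from 80% to 99%, and the full-width reading makes the miss larger. It does depend on prevalence being near the plan's 20%. That the prevalence step was left out is the likely explanation but is inferred.

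**What to change.** Remove the claim of precision within 5% for sensitivity and restate it from the expected number of positive scars. Suggested wording:

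> With 150 evaluable patients and 20% prevalence, about 30 scars are expected to be histology-positive. For an observed sensitivity of 90%, the two-sided 95% Wilson interval would be about 74% to 97% (Wald half-width about 11 points). If all 200 enrolled patients are evaluable, about 40 positives would give about 77% to 96% (about 9 points).

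State the confidence level and specify Wilson or exact intervals for the analysis, since the Wald interval performs poorly with 30 observations and a proportion near 0.9. It would help to add the expected precision for specificity and overall accuracy, with the value assumed for each.

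The cost is one rewritten paragraph and a less favourable stated precision; accrual stays at 200. If the sponsor regards 5 points as essential, rewording is not enough. The study would need about 695 evaluable patients (about 927 enrolled with the same loss allowance), or a population with a higher prevalence. That choice is the sponsor's.

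### Does the primary endpoint leave open whether the live call or the photograph read is scored?

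*Combined protocol and SAP*

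**What the plan says.** The primary endpoint, under Endpoints in the Data Analysis Plan, is "Sensitivity, specificity, accuracy for white light, white light with near focus, NBI, and NBI with near focus against histopathology as the standard reference". The sentence is complete. It gives three measures, four imaging techniques and the reference standard, but no reader.

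The Methods describe two occasions on which a scar is judged.

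- **Live.** The prior resection site is examined with the four techniques in turn, the last being "4) NBI with near focus in real time". The endoscopist answers a two-item questionnaire (suspicion of residual tumor, and confidence) during the procedure.
- **Offline.** "A total of at least four photographs will be taken for each subject to be reviewed offline blinded to histopathology". Later in the Methods, "other gastroenterologists will evaluate the photographs that were taken using different endoscopic imaging techniques", and "Same questionnaire will also be utilized".

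Between these two descriptions comes a list of data items headed "The following information are collected prospectively from study participants". It includes a positive/negative result for each of the four techniques, a high/low suspicion rating per technique, and a positive/negative histology result.

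The Power Statement says "In order to achieve confidence intervals < 5%, assuming 90% sensitivity, 150 cases are needed". It then raises enrolment to 200 to allow for drop-out, poorer images and failure to obtain four good images.

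**The concern.** In a diagnostic accuracy study the index test is a particular reader's call made under particular conditions. Here two kinds of call exist, and the endpoint sentence picks neither. They are not interchangeable. The live read is one endoscopist making all four calls in one session with the scar in view. The photograph read depends on image quality and involves other readers, with no visible number per scar.

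The text also gives each read some support. The Background hopes that "additional treatment or biopsy at the previous EMR may be avoided", a decision taken at the colonoscopy, which fits the live read. The enrolment allowance mentions image quality, which a live call does not need.

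If the choice really were open, it could be made after histology was known. If several photograph readers per scar were pooled as though independent, the intervals would look narrower than the number of scars supports. Either would weaken the primary result.

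**Working it through.** The question is mainly one of reading the text. A short calculation then shows how much precision depends on the answer.

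**Step 1: match the endpoint to the data listed.** The endpoint needs, per scar, one binary call for each of four techniques and one binary histology result.

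| Needed for the endpoint | Prospective data list (Methods) | Photograph read (Methods) |
|---|---|---|
| White light call | listed, positive/negative | no field listed |
| White light near focus call | listed, positive/negative | no field listed |
| NBI call | listed, positive/negative | no field listed |
| NBI near focus call | listed, positive/negative | no field listed |
| Histology | listed, positive/negative | same reference |

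The list follows the account of the live procedure, the biopsies and the histology, and precedes the first mention of the other gastroenterologists. Its entries carry no reader label, so this is an inference, but the list maps one-to-one onto the endpoint. For the offline read, the text says only that the questionnaire is reused. The questionnaire as worded asks about suspicion at the site, and nothing states that photograph readers answer it separately for each technique. That is plausible but not established.

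**Step 2: weigh the allowance.** It combines drop-out with image quality, states no exclusion rule and assigns no read to the primary endpoint. Photographs are part of the study whichever read is primary, so allowing for poor ones is compatible with a secondary photograph read.

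**Step 3: precision under each read.** Inputs from the Power Statement: prevalence 20%, sensitivity 90%, 150 cases, 200 enrolled. Assumed: a 95% two-sided level (none is stated), the simple normal interval and one call per scar. The half-width is h = 1.96 × √(p(1−p)/n), with n the number of scars that have residual neoplasia.

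- The plan's own figure: n = 150 gives 1.96 × √(0.09/150) = 0.048, or ±4.8 points. So 150 meets the stated target if all 150 are positive scars. The smallest such n is 1.96² × 0.09/0.05² = 138.3, rounded up to 139.
- The allowance: 150/200 = 0.75, so the step to 200 covers a 25% loss.
- All 200 usable: 0.20 × 200 = 40 positives; h = 1.96 × √(0.09/40) = 0.093, or ±9.3 points.
- 150 usable: 0.20 × 150 = 30 positives; h = 1.96 × √(0.09/30) = 0.107, or ±10.7 points.

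A live read loses no scars to image quality but can lose some to drop-out, so it lies between these two values. A photograph read that uses up the whole allowance sits at ±10.7. The difference due to the choice of read is therefore at most 10.7 − 9.3 = 1.4 points.

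That both values exceed 5 points comes from applying 20% prevalence to 150 or 200 patients. It is a separate sample-size matter and is the same for either read.

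**The case for a change.** The strongest case for a change is that the primary endpoint line is complete and names no reader, two sets of reads are certainly planned, and one sentence would settle it at no cost in patients or procedures. A later list that placed the photograph read among the secondary endpoints would settle the matter only by implication. All of that is true, and a named read would be tidier.

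What does not stand is the harm.

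- Inflated error from choosing the read after seeing both requires a significance test and a choice made after the results. The visible primary endpoint is estimation, the sample size is based on precision, and no test or significance level appears.
- Intervals that are too narrow require several photograph readers per scar, treated as independent, as the primary analysis. No passage plans this. The Power Statement counts cases, which fits one call per scar.
- A rule that poor photographs must not remove a scar from the live analysis would guard against an exclusion that the plan does not state.

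One part cannot be sized. Live and photograph reads may have different true sensitivities, and the documents give no figure for either. That is a reason to report both reads under clear labels, which the two-part design already makes natural.

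**Conclusion.** The omission is real but harmless: it is a gap that a competent analyst fills from the plan itself. The data list, the stated clinical purpose and the case-based sizing all point to the live per-technique calls as the primary index test, with the photograph read as supporting evidence. Followed that way, no stated rule gives a wrong result. If photographs turn out to be read by more than one person, treating the scar as the unit is ordinary practice and needs no instruction here.

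The effect on precision is at most 1.4 points of half-width (±9.3 against ±10.7), given the plan's 20% and 90%, a 95% level and one call per scar. The reading rests on an unlabelled list rather than an explicit statement. It also rests on a text that ends at the heading for secondary endpoints, so what followed is unknown and cannot be counted against the plan.
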